-Number of episodes of neurological deterioration in both groups of patients during the 12 days of treatment.

- Symptoms associated with TBI in both groups of patients during the 12 days of treatment.
- Volume of pericontusional edema before and after 12 days of treatment in both groups of patients.
- Presence of adverse events between the two groups during the 12 days of treatment.
- Neuropsychological tests between the two groups of patients one month and 6 months after the TBI.

Estimated event rate

In our previous studies we have described that among TBI patients with brain contusions not treated with dexamethasone, the proportion of patients with good recovery (GOSE 7 and 8) was 50%.

Sample size and treatment effect size that should be detectable

Since the data available in this type of patients with this treatment is scarce and inconclusive, we will perform a randomized, triple-blind, placebo controlled trial with an interim futility analysis (interim analysis). The primary endpoint for the DEXCON TBI trial is the good recovery (GOSE 7-8) one month after the TBI.

A study with 600 patients would have about 80% power (two sided alpha=5%) to detect a 12% absolute increased (from 50% to 62%) in good recovery (GOSE 7-8). It includes an inflation of 10% due to non-adherence (withdrawal of consent, loss to follow-up, cross-over or change of treatment).

Recruitment of collaborating investigators

The trial will recruit hospitals from Spain. Suitable collaborating hospitals and investigators will be assessed in terms of the trauma service that they provide and their ability to conduct the trial.

Before the trial can begin at any site, the local Principal Investigator must agree to adhere to Good Clinical Practice Guidelines and all relevant national regulations. In addition, all relevant regulatory and ethics approvals should be in place before the trial starts at a site.

Ethical considerations, information giving and written informed consent

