The purpose of the sliding dichotomy approach is to increase the sensitivity (to lower the false negative rate) of the analysis. All these variables will also be analyzed in a pre-specified subgroup analysis comparing patients with a pericontusional edema volume of more than 10 mL in the pre-inclusion computed tomography (CT) scan in the study with those who have less than 10 mL of edema volume in the same CT study.

Interim analysis

Since the data available in this type of patients receiving this treatment are scarce and inconclusive as to the primary outcome variable, we will perform an interim analysis. A statistician ([name]) will blindly perform an interim analysis calculating the conditional power, an approach that quantifies the probability of obtaining a significant result at the end of the study given the data available after one year enrolling patients.

Since the probability chosen for futility in this trial is very small (< 0,15), it can be concluded that it would be useless to continue the trial. This interim analysis will be performed at the end of the first year since the inception of the trial, when it is estimated that about 100 patients will have been recruited. At the same time, a safety analysis will be also performed, focused on the adverse effects collected during the first year.

The results will be assessed and discussed by an independent Data Monitoring Committee, formed by one statistician and two experts in TBI, who will inform and make recommendations to the Trial Steering Committee, which will finally make the decisions.

Follow-up

No extra tests are required for the trial but a case report form should be completed at the end of the 12- day treatment, or at death or hospital discharge if either happens sooner. The GOSE and the neuropsychological evaluations will be performed one month and 6 months after the TBI. Both evaluations will be performed by clinical

neuropsychologists, and the protocol used will always follow the same process. The neuropsychological tests that will be performed are described in the Supplemental data

Sponsorship and trial management

This research project has no sponsor. The trial will be coordinated by the Trial Steering Committee (TSC).

Indemnity

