FIGURE 1. TRIAL OVERVIEW

[figure not shown]
[figure not shown]

FIGURE 2. MEASURES OF OUTCOME DURING THE TRIAL

Inclusion CT: CT performed in the previous 24 hours before randomisation

End of treatment CT: CT performed in the following 48 hours after treatment period

GOSE: Glasgow Outcome Scale Extended

RPQ: Rivermead post-concussion symptoms questionnaire

TIL: Therapy Intensity Level

NT: Neuropsychological tests: QLIBRI, MOCA, RAVL-T, Coding WAIS IV, CPT, STROOP, TOLDX, Digit span WAIS IV

SUPPLEMENTAL DATA 1.

Primary Outcome measurement

The primary outcome is the Glasgow Scale Outcome Extended (GOSE) performed one month and 6 months after trauma. This scale will be dichotomized in favorable outcome (GOSE 7-8 points) and unfavorable recovery (GOSE≤6 points)

Secondary Outcome measurements

-Compare the number of episodes of neurological deterioration in both groups of patients during the 12 days of treatment.

The number of episodes of neurological impairment will be detected by the Glasgow coma scale and the abbreviated NIHSS scale, during the 12 days of treatment.

An episode of neurological impairment is defined as a worsening of at least 2 points on the Glasgow coma scale or the NIHSS scale, which lasts at least 2 hours, and which cannot be fully attributed to other causes other than that cerebral edema. In order to rule out other causes of neurological deterioration, complementary tests will be performed according to the protocol of action of each hospital. Among these tests are an arterial blood gas analysis, blood test with blood count and biochemistry, electroencephalogram and a cranial CT scan.

Baseline scores to compare subsequent neurological examinations will be performed 30 minutes before starting the study medication. Subsequently, the reference scores will depend on the patient's clinical evolution. After sustained episodes of improvement or worsening in the patient's clinical situation, the baseline scores will be recalculated to reflect the best score of the Glasgow coma scale and the NIHSS before a possible episode of neurological impairment. In those patients in whom it is not possible to perform neurological examinations, the reason will be collected in the Investigator's Study File.

The neurological exams will be performed 3 times per day during the 12 days of treatment.

-Compare the symptoms associated with TBI in both groups of patients during the 12 days of treatment.

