The symptoms associated with TBI will be studied daily through the Rivermead Post Concussion Symptom (RPQ) scale. The RPQ is a questionnaire that measures the severity of symptoms associated with TBI. The questionnaire contains 16 symptoms and the patient is asked to quantify these symptoms during the past 24 hours.

In each case, the symptoms are compared with the severity of these symptoms before the trauma. The symptoms range from 0 to 4 points: 0: it has not presented such a symptom; 1: it has not been a bigger problem than before the TBI; 2: slight problem; 3: moderate problem; 4: serious problem.

The RPQ scale will be performed once daily during the 12 days of treatment.

-Compare the volume of pericontusional edema before and after 12 days of treatment in both groups of patients.

In each center, researchers will record the volume of the lesions including the hemorrhagic portion and the pericontusional edema using the ABC / 2 methodology. In the case of multiple contusions, each of them will be measured separately up to a number of 3, starting with the largest.

The image will be analyzed using a standard window for all cases (window level 60 and width of 100 UH), thus ensuring a similar gray scale in the different centers. A measurement of the largest diameter (A) will be made in each contusion, followed by the largest perpendicular diameter to A (B) and the number of cuts in which the contusion (hyperintense area and perilesional hypodense area) can be identified (C). The total volume of the bruises will be equal to the sum of the individual volumes of each one, whose volume results from multiplying the three diameters and dividing them by two. Once this process has been carried out, a measurement will only be made of the hyperdense portion of the contusions to establish the volume of the edema:

Edema volume = total volume-volume hyperdensity.

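### The treatment-period form is completed at discharge if that precedes day 12, but deterioration, symptoms and adverse events are defined over 12 days and no route is given for non-serious events after discharge

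*Combined protocol and SAP*

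**What the plan says.** The timing rule is in the Follow-up section, which has one form filled in when treatment finishes on day 12, "or at death or hospital discharge if either happens sooner".

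The outcomes are listed under Secondary outcomes with a fixed window:

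- Deterioration: "Number of episodes of neurological deterioration in both groups of patients during the 12 days of treatment"
- Symptom burden, listed next: "Symptoms associated with TBI in both groups of patients during the 12 days of treatment"
- Safety, listed later: "Presence of adverse events between the two groups during the 12 days of treatment"

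Supplemental data 1 sets the schedule that feeds them: "The neurological exams will be performed 3 times per day during the 12 days of treatment" and "The RPQ scale will be performed once daily during the 12 days of treatment". It also asks for the highest capillary glucose and the insulin requirement each day. None of these has an exception for discharged patients.

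Four other places bear on the point:

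- Data collection and management takes the data from ordinary clinical records.
- Reporting of adverse events requires a written report of any serious adverse event within 24 hours, separately from this form.
- Outcome measures says that outcomes are still collected when treatment is interrupted or not given. It does not mention discharge.
- The Figure 2 legend schedules a scan after treatment: "End of treatment CT: CT performed in the following 48 hours after treatment period".

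**The concern.** The outcome window is 12 days for everyone, but the form's window is 12 days or the hospital stay, whichever is shorter. A site that follows the Follow-up section has no instruction to record a non-serious event on, say, day 10 in a patient discharged on day 7, and hospital records would not be expected to hold it. The plan gives no rule for shortened observation: no rate per day observed, no censoring rule, and no handling of death.

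Two consequences follow. First, events are under-counted in patients who leave early. This touches the safety analysis planned with the one-year interim analysis, which draws on these adverse events. Second, if the treatment changes when patients go home, the arms are observed for different lengths of time. Either direction is plausible from the plan itself. The trial hopes for better recovery at one month, which could shorten the stay. It also lists prolonged stay caused by an adverse event as something to report, which would lengthen it.

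**Working it through.** **The plan's own figure.** The only planned size is 600 patients for good recovery, 50% v 62%, two-sided 5%, about 80% power, 10% inflation. With the pooled-variance formula, n per arm = [1.96·√(2·0.56·0.44) + 0.8416·√(0.50·0.50 + 0.62·0.38)]² / 0.12² = (1.376 + 0.586)² / 0.0144, which rounds up to 268. That is 536 in total, and 536/0.90 = 596. With 540 evaluable patients (270 per arm), power is 80.4%. The figure of 600 reproduces. It rests on one-month GOSE, so this point does not change it.

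**Passages side by side.**

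| Item | Window by outcome definition | Stated route after discharge |
|---|---|---|
| Neurological deterioration | 12 days, 3 exams a day (36 scheduled) | none |
| Symptoms (RPQ) | 12 days, daily (12 scheduled) | none |
| Non-serious adverse events, daily glucose | 12 days | none |
| Serious adverse events | 12 days | separate 24-hour report |
| End-of-treatment CT | within 48 hours after treatment | own timing, not tied to the form |
| GOSE, neuropsychology | 1 and 6 months | own visits |

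The gap lies in the first three rows.

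**Illustration of size (all inputs assumed).** The documents give neither discharge shares nor 12-day event risks. Assume no drug effect, a constant daily event hazard h equal in both arms, and a constant discharge hazard d independent of events. Let R be the true 12-day risk and F the share discharged by day 12:

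- h = −ln(1−R)/12 and d = −ln(1−F)/12
- recorded risk = h/(h+d) · [1 − exp(−12(h+d))], where exp(−12(h+d)) = (1−R)(1−F)
- mean days to discharge or day 12 = F/d

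With R = 20%, h = 0.01860:

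- F = 30%: d = 0.02972; recorded 0.3848 × (1 − 0.56) = 16.9%; mean 10.1 days
- F = 40%: d = 0.04257; recorded 0.3040 × (1 − 0.48) = 15.8%; mean 9.4 days
- F = 60%: d = 0.07636; recorded 0.1958 × (1 − 0.32) = 13.3%; mean 7.9 days

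| Discharged by day 12, arm 1 v arm 2 | Recorded risk, R = 20% | Ratio at R = 10% / 20% / 30% |
|---|---|---|
| 40% v 40% | 15.8% v 15.8% | 1.00 / 1.00 / 1.00 |
| 40% v 50% | 15.8% v 14.6% | 0.92 / 0.92 / 0.93 |
| 40% v 60% | 15.8% v 13.3% | 0.84 / 0.84 / 0.85 |
| 30% v 60% | 16.9% v 13.3% | 0.78 / 0.79 / 0.79 |

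Equal discharge costs events but creates no difference: at 40%, (20 − 15.8)/20 = 21% of first events go unrecorded in both arms. Unequal discharge creates a ratio close to the ratio of mean days observed (7.86/9.40 = 0.84 for 40% v 60%). Following everyone to day 12 restores 20% v 20%.

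**The case against.** The strongest reply is that the Follow-up section says when a form is completed, not that observation ends. Supplemental data 1 still calls for exams and symptom scores through day 12 without exception, and participation runs to death or six months. This stands in part: the documents contradict each other and do not clearly cut observation short. But the contradiction has to be resolved, because the only stated completion rule points to discharge and no other route is given for non-serious events. The 24-hour report does not fill the gap. It covers serious events only, and events expected from the brain injury itself are not to be reported as adverse events.

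A reader might infer several stronger things that the documents do not support:

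- **That the arms will be observed for unequal, treatment-dependent times.** This needs discharge timing to differ by arm. No discharge data are given, and with equal discharge the ratio stays at 1.00.
- **That early discharge will be common because half of untreated patients are expected to reach GOSE 7-8.** The sample-size endpoint is GOSE at one month, which does not fix who leaves before treatment day 12.
- **That the end-of-treatment scan is lost.** It has its own timing, after the treatment period, even for patients who stay in hospital throughout.
- **That completion of treatment, which the Analysis section uses to define the primary analysis set, cannot be verified after discharge.** Labelled containers and an instruction sheet are compatible with dosing at home, but the plan does not state it. It is silent on capsule accountability, and silence does not show that verification is impossible.
- **That episodes will be compared as raw counts.** The plan names the outcome and gives no model for it.

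A further fair point is that modelling events per observed day does not cure bias if patients leave because they are well or stay because they are not. That is why complete ascertainment is the main remedy and the rate analysis only a sensitivity analysis.

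**Conclusion.** The point holds as an unreconciled conflict between the form's timing and the outcome window, with a missing route for non-serious events after discharge. Followed as written, the form under-counts deterioration, symptoms and adverse events in patients discharged before day 12. A bias between arms is possible, and its direction is unknown.

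The sizes rest wholly on assumed discharge shares and risks, constant hazards and discharge independent of events. Across the unequal scenarios shown, the spurious ratio runs from about 0.92 to 0.78, and it is 1.00 when discharge is equal. The scope is the in-treatment secondary and safety outcomes. GOSE collection, the 600 patients and the power are unaffected. It is worth correcting because the remedy is cheap and post-discharge events are hard to reconstruct later.

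**What to change.** 1. In Follow-up, have the form completed at day 12 for every living patient, discharged or not, and at death for those who die earlier. This reconciles it with Secondary outcomes and Supplemental data 1.
2. For discharged patients, use the end-of-treatment CT contact (day 12 plus up to 48 hours, so days 12 to 14) to record adverse events and deterioration since discharge, limited to events up to day 12, and the capsule count.
3. Add a field for the last day of direct observation, and report days observed by arm.
4. In Analysis, compare these outcomes over the full 12 days, and pre-specify event rates per observed day as a sensitivity analysis, with death handled as a competing event.

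The cost is one changed sentence, a few form fields and a short addition to the analysis text; no new visit is needed. The downside is that post-discharge events rest on recall. The three-times-daily exams and the daily RPQ cannot be recreated after discharge, so deterioration and symptoms should always be reported alongside days observed.

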FIGURE 1. TRIAL OVERVIEW

[figure not shown]
[figure not shown]

FIGURE 2. MEASURES OF OUTCOME DURING THE TRIAL

Inclusion CT: CT performed in the previous 24 hours before randomisation

End of treatment CT: CT performed in the following 48 hours after treatment period

GOSE: Glasgow Outcome Scale Extended

RPQ: Rivermead post-concussion symptoms questionnaire

TIL: Therapy Intensity Level

NT: Neuropsychological tests: QLIBRI, MOCA, RAVL-T, Coding WAIS IV, CPT, STROOP, TOLDX, Digit span WAIS IV

SUPPLEMENTAL DATA 1.

Primary Outcome measurement

The primary outcome is the Glasgow Scale Outcome Extended (GOSE) performed one month and 6 months after trauma. This scale will be dichotomized in favorable outcome (GOSE 7-8 points) and unfavorable recovery (GOSE≤6 points)

Secondary Outcome measurements

-Compare the number of episodes of neurological deterioration in both groups of patients during the 12 days of treatment.

The number of episodes of neurological impairment will be detected by the Glasgow coma scale and the abbreviated NIHSS scale, during the 12 days of treatment.

An episode of neurological impairment is defined as a worsening of at least 2 points on the Glasgow coma scale or the NIHSS scale, which lasts at least 2 hours, and which cannot be fully attributed to other causes other than that cerebral edema. In order to rule out other causes of neurological deterioration, complementary tests will be performed according to the protocol of action of each hospital. Among these tests are an arterial blood gas analysis, blood test with blood count and biochemistry, electroencephalogram and a cranial CT scan.

Baseline scores to compare subsequent neurological examinations will be performed 30 minutes before starting the study medication. Subsequently, the reference scores will depend on the patient's clinical evolution. After sustained episodes of improvement or worsening in the patient's clinical situation, the baseline scores will be recalculated to reflect the best score of the Glasgow coma scale and the NIHSS before a possible episode of neurological impairment. In those patients in whom it is not possible to perform neurological examinations, the reason will be collected in the Investigator's Study File.

The neurological exams will be performed 3 times per day during the 12 days of treatment.

-Compare the symptoms associated with TBI in both groups of patients during the 12 days of treatment.

The symptoms associated with TBI will be studied daily through the Rivermead Post Concussion Symptom (RPQ) scale. The RPQ is a questionnaire that measures the severity of symptoms associated with TBI. The questionnaire contains 16 symptoms and the patient is asked to quantify these symptoms during the past 24 hours.

In each case, the symptoms are compared with the severity of these symptoms before the trauma. The symptoms range from 0 to 4 points: 0: it has not presented such a symptom; 1: it has not been a bigger problem than before the TBI; 2: slight problem; 3: moderate problem; 4: serious problem.

The RPQ scale will be performed once daily during the 12 days of treatment.

-Compare the volume of pericontusional edema before and after 12 days of treatment in both groups of patients.

In each center, researchers will record the volume of the lesions including the hemorrhagic portion and the pericontusional edema using the ABC / 2 methodology. In the case of multiple contusions, each of them will be measured separately up to a number of 3, starting with the largest.

The image will be analyzed using a standard window for all cases (window level 60 and width of 100 UH), thus ensuring a similar gray scale in the different centers. A measurement of the largest diameter (A) will be made in each contusion, followed by the largest perpendicular diameter to A (B) and the number of cuts in which the contusion (hyperintense area and perilesional hypodense area) can be identified (C). The total volume of the bruises will be equal to the sum of the individual volumes of each one, whose volume results from multiplying the three diameters and dividing them by two. Once this process has been carried out, a measurement will only be made of the hyperdense portion of the contusions to establish the volume of the edema:

Edema volume = total volume-volume hyperdensity.

This procedure will be performed again centrally in the 12 de Octubre hospital, Madrid. Previously, the patient's data will be anonymized and the images will be sent through a web platform with a secure server for review. In a central way, the total volume of the contusion will be established as well as the volume of the edema by means of a semi-automatic method using the Analyze software (vesion 10.0; Analyze Direct, Stilwell, Kansas, USA) of which a license is available. The method consists of a semi-automatic analysis in which in each axial section a central voxel is selected and thanks to the density selection, voxels with similar density characteristics are selected.

The performance of measurements in each hospital and subsequent centralization of the images will allow to establish the interobserver and intermethod reproducibility of the measurement of the edema associated with the contusions, in addition to estimating in two ways the difference of measurements at two time points throughout the study and after an intervention.

-Compare the presence of adverse events between the two groups during the 12 days of treatment.

Those adverse effects that have special interest and serious adverse effects will be collected. Side effects of special interest are:

-Metabolic: Hyperglycemia will be especially monitored. The maximum value of capillary glycemia will be recorded daily. The amount of daily insulin that the patient needs to control de glucose level will also be collected.

-Psychiatric: presence of psychotic symptoms using the Confusion Assessment Method (CAM).

-Digestive: Episodes of gastro intestinal hemorrhage; Episodes of epigastric pain, vomiting or reflux symptoms.

-Infectious: Presence of new infectious episodes. Infectious episode will be confirmed in accordance with the Centers for Disease Control (CDC) criteria and mainly based on microbiological criteria.

- Compare the results of the neuropsychological tests between the two groups of patients one month and 6 months after the TBI.

Two neuropsychological evaluations will be performed: 1 month and 6 months after the TBI. Both evaluations will be performed by clinical neuropsychologists, and the protocol to be used will always follow the same procedure and tests. The tests that integrate this protocol are described below:

-The MOCA (Montreal Cognitive Assessment): originally designed as a rapid screening instrument for mild cognitive dysfunction. It assesses different cognitive domains: attention and concentration, executive functions, memory, language, visuoconstructional skills, conceptual thinking, calculations, and orientation.

- Rey Auditory Verbal Learning Test (RAVLT) is one of the most widely used word learning tests in clinical research and practice. Five presentations of a 15-word list are

given, each followed by attempted recall. This is followed by a second 15-word list (list B), followed by recall of list A, and delayed recall and recognition are also tested.

- Coding (WAIS-IV Battery subtest): essentially aims to assess processing speed, associative memory, graphomotor speed.
- Computerized Continuous Continued Test (CPT) The CSAT-II RESEARCH VERSION: this version is used to evaluate sustained attention, discrimination, types of errors made, motor response style and response speed during the task.
- Stroop test: This is a psychological test linked especially to neuropsychology that measures measuring the level of interference generated by automatisms in the performance of a task.
- Digit Span (WAIS-IV Battery subtest): essentially measures auditory working memory and your ability to record, maintain and manipulate auditory information consciously.
- Test Tower of London-Drexel University version test (TOLDX): measures executive planning ability in subjects with frontal lobe injury. Traditionally used as a planning and problem-solving measure.
- Quality of Life after brain injury (QOLIBRI) Spanish version: to measure quality of life after TBI. Through these scales and questionnaires, what is intended is to obtain information obtained, preferably, from the patient himself and simultaneously from a family member or friend (proxy) in order to corroborate the information provided by the patient himself.

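### The site ABC/2 rule takes C as a count of CT cuts without slice thickness, so site edema volumes computed as written depend on how thick the slices are

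*Combined protocol and SAP*

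**What the plan says.** All the measurement rules are in Supplemental data 1, under the secondary outcome on pericontusional edema volume.

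- **Site reading.** At each center, "researchers will record the volume of the lesions including the hemorrhagic portion and the pericontusional edema using the ABC / 2 methodology". A is the largest diameter and B the largest diameter perpendicular to it. C is "the number of cuts in which the contusion (hyperintense area and perilesional hypodense area) can be identified (C"). Each contusion has a volume "whose volume results from multiplying the three diameters and dividing them by two".
- **Edema.** The hyperdense part is then measured on its own, and "Edema volume = total volume-volume hyperdensity".
- **What is standardised.** The plan fixes a "standard window for all cases (window level 60 and width of 100 UH), thus ensuring a similar gray scale in the different centers". It says nothing about slice thickness or spacing.
- **Central reading.** "This procedure will be performed again centrally in the 12 de Octubre hospital, Madrid", but by a different technique: total contusion volume and "the volume of the edema by means of a semi-automatic method using the Analyze software", which selects voxels by density. The two sets of readings are to serve a reproducibility study and to give two estimates of the change over time.
- **Subgroup.** The Analysis section pre-specifies a subgroup comparison that separates patients with a "pericontusional edema volume of more than 10 mL in the pre-inclusion computed tomography (CT) scan" from those with less. It does not say whether the site or the central reading decides.

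**The concern.** ABC/2 approximates an ellipsoid and needs three lengths. The text supplies two lengths and a count, then treats all three as diameters. A count of cuts becomes a height only when multiplied by slice thickness. Without that step the same lesion gets a different site volume on every slice protocol.

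Three planned uses could be touched:

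1. **The edema-volume secondary outcome.** Thickness may differ between the inclusion CT and the end-of-treatment CT.
2. **The site-versus-central comparison.** It is meant to measure agreement between readers and methods, not a unit error.
3. **The 10 mL subgroup.** A fixed cut in mL needs a scale that really is in mL.

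The scope for variation is real. The trial starts at two hospitals and may open to a network of 56 (Settings), and the protocol relies on routine care without extra tests (Data collection and management; Follow-up).

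**Working it through.** The plan gives no worked volume, slice thickness or subgroup count, so there is no figure of its own to reproduce. The check is direct geometry.

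**Inputs from Supplemental data 1:** C is the number of cuts *n*; volume = A × B × C / 2; edema = total minus hyperdense volume.

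**Assumptions:** A and B are in cm (no unit is given). Slice thickness *t* runs from 0.1 to 1.0 cm, that is 1 to 10 mm (none is given). The same count rule is used for the total and the hyperdense measurement.

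**Scale factor.**
- As written: A × B × n / 2.
- With thickness: A × B × (n × t) / 2, in mL.
- Ratio, written to correct: 1/t with t in cm, which is 10 mm divided by slice thickness.
- Edema is the difference of two such products from one scan, so it carries the same factor.

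**Example (assumed lesion).** Total 4 × 3 cm with height 4 cm; hyperdense part 2 × 2 cm with height 2 cm. Correct edema volume = 4 × 3 × 4 / 2 − 2 × 2 × 2 / 2 = 24 − 4 = 20 mL.

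| Slice thickness (assumed) | Cuts, total / hyperdense | Edema as written | Ratio | Correct volume when the rule reads 10 |
|---|---|---|---|---|
| 1 mm | 40 / 20 | 240 − 40 = 200 | 10 | 1.0 mL |
| 2.5 mm | 16 / 8 | 96 − 16 = 80 | 4 | 2.5 mL |
| 5 mm | 8 / 4 | 48 − 8 = 40 | 2 | 5.0 mL |
| 10 mm | 4 / 2 | 24 − 4 = 20 | 1 | 10.0 mL |

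**Change between scans.** Take an edema that stays at 8 mL.
- 2.5 mm then 5 mm: 8/0.25 = 32, then 8/0.5 = 16, a change of −50%.
- 5 mm then 2.5 mm: 16, then 32, a change of +100%.
- Same thickness at both scans: the percentage change is correct, but the absolute change is still multiplied by 1/t.

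This 8 mL lesion belongs below the 10 mL cut, yet the written rule gives 16 or 32 and would place it above.

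**Unit assumption.** If A and B were taken in mm and the product divided by 1,000, the factor would be 1/t with t in mm: 1 at 1 mm, 0.4 at 2.5 mm, 0.2 at 5 mm and 0.1 at 10 mm. The direction of the error therefore depends on the unit. The false percentage change between scans does not, because the unit cancels.

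**With C = cuts × thickness,** the ratio is 1 at every thickness. The central voxel method does not use C, so it is outside this calculation.

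**The case against.** The strongest reply is that this is loose wording. Naming the ABC/2 method and calling all three terms diameters suggests that a length was meant, and sites may already multiply by thickness. That is plausible, but C is defined explicitly, and a site that follows the definition gets a mis-scaled result. If some sites multiply and others do not, the site data are inconsistent as well.

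A second reply is that the central reading protects the trial. This stands for the central series. It does not clear the site series, because Supplemental data 1 keeps it as one of the two estimates of change, and no section names either reading as the one that counts.

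A third reply is that the consequences are limited. This also stands. Edema volume is one of five secondary outcomes, and the cut defines one subgroup comparison. Each hospital has its own randomization list in blocks of two, so scanner differences between hospitals should be roughly balanced between arms. Nothing in the documents shows that thickness actually differs between the two CTs. A several-fold gap between site and central volumes would probably be noticed in the reproducibility study.

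A reader might infer that the trial's edema volumes and the 10 mL subgroup are simply wrong. The documents do not support that: they report no volumes, the central volume is independent of C, and the Analysis section does not tie the subgroup to the site reading.

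**Conclusion.** The point holds for the site ABC/2 volumes and is conditional on the rule being applied as written. With A and B in cm, the inflation is 10 mm divided by slice thickness, or 10-fold down to 1-fold over an assumed 1 to 10 mm. A change of thickness between scans produces a false change in edema: −50% or +100% for 2.5 and 5 mm slices. The reproducibility comparison would mix this scaling artefact with true disagreement.

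The 10 mL subgroup is at risk only if the site reading defines it, and leaving that open is a gap of its own. The primary GOSE outcome and the sample size do not use these volumes. Expect noise and misclassification rather than bias between arms. The rule should be corrected before site volumes are analysed, but it does not threaten the main conclusion of the trial.

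**What to change.** 1. In Supplemental data 1, define C as the number of cuts multiplied by slice thickness (spacing), in cm, for both the total and the hyperdense measurement. State that A and B are in cm.
2. Record slice thickness for each CT on the CRF. For patients already enrolled, recover it from the stored images.
3. State in the Analysis section that the central semi-automatic volume is the main edema-volume reading and defines the 10 mL subgroup. Keep the corrected site ABC/2 volume as the second estimate of change that Supplemental data 1 already plans, and for the reproducibility study.

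The cost is a few sentences, one CRF field for each CT, and a recalculation of site volumes already recorded. No extra reading is needed, because the central measurement is already planned.
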